3.3 Randomization

Patients will be randomly allocated to the conventional treatment (control) or UC-MSC treatment (UC-MSC infusion) groups at a 1:1 ratio according to a computer-generated randomization list. The randomization list will be generated by third party statistical staff. The randomization code will be assigned to a participant at his or her first visit. The participants will be assigned to the treatment groups corresponding to the randomization code. This is an open-label study; both participants and the study team will be aware of the treatment allocation.

4 Participants

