12.2 Definition and selection of analysis sets

This study used three data sets: A safety set, a full analysis set, and a per-protocol set.

Safety set (SS): SS refers to the set of all subjects who received at least one UC-MSC infusion and had a post-treatment safety record. The SS will be used for safety analysis and the subjects will be analyzed according to the actual treatment received.

Full analysis set (FAS): FAS refers to the set of all subjects who randomly received at least

one UC-MSC infusion. When the main efficacy indicators are missing, the missing data is not filled in, and will be assigned to the unresponsive set. FAS is the primary analysis set and will be used to report the distribution, demographic data, baseline characteristics, compliance, and efficacy evaluation for all subjects. The subjects will be analyzed in a randomized treatment group.

Per-protocol set (PPS): PPS refers to the set that the subjects coincide with the major inclusion criteria, do not coincide with the major exclusion criteria, complete the treatment regimen, do not take banned medication during the trial, and have no other major program violations. PPS will be used to evaluate primary efficacy.

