12.3.4 Efficacy analysis

The efficacy analysis will be based on the FAS set. PPS analysis will serve as an ancillary analysis for FAS. If the PPS results are inconsistent with the FAS results, it will be necessary to analyze and discuss the possible causes.

(1) Primary efficacy

All eligible participants who receive the assigned treatment and are followed up will be included in the analysis. We will count the number of endpoint events (death or HCC events) that occurred during the follow-up period and will compare the event-free time between the two groups using Kaplan–Meier analysis. The post-treatment follow-up will be continued until the date of an endpoint event, death, or the end of the study, whichever occurs first. Cox proportional-hazards models will be developed to estimate the hazard ratio (HR) and 95% confidence interval (CI) for between-group comparisons, with or without adjustments for stratification baseline MELD scores. Additionally, we will perform landmark analyses to assess the endpoint events accordingly, with the hazard ratio calculated separately for events that occurred before or after the landmark points.

(2) Secondary efficacy indicators

Liver function: The serum levels of ALB, PTA, CHE, and TBIL will be monitored within 48 weeks after the first UC-MSC infusion or routine medical treatment. A paired t-test will be applied to analyze the levels of ALB, PTA, CHE, and TBIL of the participants in each group post-treatment compared with those at baseline. The levels of ALB, PTA, CHE, and TBIL of the participants will also be compared between the treatment group and the control group at each specific evaluation timepoint. Student's t test or a non-parametric test will be applied when relevant.

Complications: MedDRA will be used to code and classify complications. For all cases, the

episode and severity of the complication will be listed by groups. The incidence by each study group and severity, respectively, will be calculated. The incidence between groups will be compared using the Chi-squared test or Fisher's exact test. Multiple Chi-squared comparisons will be performed on the basis of a Bonferoni-adjusted α value when relevant.

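### The primary analysis set is defined by receiving a UC-MSC infusion: no control can meet it as written, and the natural repair drops never-infused patients from one arm only

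*Protocol*

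**What the plan says.** Section 12.2 defines the full analysis set in one sentence that runs over a page break. It begins "FAS refers to the set of all subjects who randomly received at least". After the break, the entry condition is completed and a rule for missing data follows: "one UC-MSC infusion. When the main efficacy indicators are missing, the missing data is not filled in". The same paragraph gives the set its role, "FAS is the primary analysis set and will be used to report the distribution, demographic data, baseline characteristics, compliance, and efficacy evaluation for all subjects", and says how patients are grouped within it: "The subjects will be analyzed in a randomized treatment group".

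Section 12.3.4 opens with "The efficacy analysis will be based on the FAS set". Its paragraph on primary efficacy then gives another population: "All eligible participants who receive the assigned treatment and are followed up will be included in the analysis".

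Section 12.2 defines the per-protocol set (PPS) as patients who, among other things, "complete the treatment regimen, do not take banned medication during the trial, and have no other major program violations", and assigns that set to the evaluation of primary efficacy. Section 12.3.4 makes it ancillary to the FAS.

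Section 3.1 gives controls conventional treatment alone, with no infusion of any kind. Sections 7.1 and 9 count survival and time to HCC from the first infusion. On timing, Section 3.3 says "The randomization code will be assigned to a participant at his or her first visit", and that allocation is known to patients and study team. Section 6.3 lists a repeat check of eligibility at week 0, ahead of the infusion.

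**The concern.** Entry to the primary analysis set depends on a treatment that only one arm can receive. There are two consequences, one for each way of reading the rule.

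Taken literally, the set has no controls and the two-group Kaplan-Meier and Cox comparison has nothing to compare. If controls are let in without a condition, the infusion requirement remains for the UC-MSC arm. A patient allocated to UC-MSC who deteriorates, dies, refuses or fails the repeat eligibility check before week 0 leaves the analysis. A similar patient allocated to control stays in. The comparison is then no longer between the groups as randomised, and the exclusions can depend on prognosis.

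The endpoints are overall survival and HCC-free survival, where a few early exclusions of sick patients can matter. With several populations in the text and no blinding, the choice among them would be open to settlement once outcomes are known.

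**Working it through.** **The passages side by side.**

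| Place | Who is in | Can a control qualify? | Depends on events after randomisation? |
|---|---|---|---|
| 12.2, FAS | at least one UC-MSC infusion | no, as written | yes |
| 12.3.4, primary efficacy | eligible, got the assigned treatment, followed up | yes | yes |
| 12.2, PPS (primary efficacy there, ancillary in 12.3.4) | completed the regimen, no major violation | yes | yes |

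No section gives an all-randomised analysis or an FAS entry rule for controls. Grouping as randomised fixes the arm label of those included, not who is included. Literal count: at most 125 UC-MSC patients against 0 controls, out of 125 + 125 = 250.

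**The plan's own figure.** Section 12.1 claims more than 80% power with 100 per group at two-sided 0.05. Its sentence on rates is garbled; I read it as 60% and 85% event-free at 60 months (assumption).
- HR = ln(0.85)/ln(0.60) = 0.318.
- Two proportions: pooled p = 0.725; SE0 = √(2 × 0.725 × 0.275/100) = 0.0631; SE1 = √((0.24 + 0.1275)/100) = 0.0606; z = (0.25 − 1.96 × 0.0631)/0.0606 = 2.08, so power is 98%. The claim is met.
- 100/(1 − 0.20) = 125, so the stated 125 per group fits a 20% loss.

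The present point does not depend on this figure. Only the 60% control rate and the 125 per group carry forward.

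**Size of the selection under the natural repair.** Let f be the share of the UC-MSC arm never infused and s0 the share of those patients event-free at 60 months. The protocol gives neither, so both are assumptions. With no true effect and 60% event-free in both arms as randomised:
- event-free share among the infused: s = (0.60 − f·s0)/(1 − f);
- apparent HR = ln(s)/ln(0.60);
- type I error: two-sided 5% test of s against 0.60, with 125(1 − f) against 125 patients.

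Example, f = 10% and s0 = 0: s = 0.60/0.90 = 0.667. HR = ln(0.667)/ln(0.60) = 0.79. The difference is 0.067, with SE0 = 0.0627 and SE1 = 0.0624. Upper tail: Φ((0.067 − 1.96 × 0.0627)/0.0624) = Φ(−0.90) = 0.184. The lower tail adds 0.001, giving 18.5%.

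| f | s0 | s | Apparent HR | UC-MSC n (expected) | Type I error |
|---|---|---|---|---|---|
| 5% | 0.60 | 0.600 | 1.00 | 118.75 | 5% |
| 5% | 0.40 | 0.611 | 0.97 | 118.75 | 5.3% |
| 5% | 0.20 | 0.621 | 0.93 | 118.75 | 6.3% |
| 5% | 0 | 0.632 | 0.90 | 118.75 | 8.0% |
| 10% | 0.60 | 0.600 | 1.00 | 112.5 | 5% |
| 10% | 0.40 | 0.622 | 0.93 | 112.5 | 6.4% |
| 10% | 0.20 | 0.644 | 0.86 | 112.5 | 10.8% |
| 10% | 0 | 0.667 | 0.79 | 112.5 | 18.5% |

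This is a fixed-time calculation at 60 months, meant to show scale. It does not predict what the trial will see.

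**The case against.** The strongest reply is that the FAS sentence is a slip. Section 12.2 speaks of all subjects and of randomised groups, 12.3.1 tabulates the sets by group, and 12.3.4 compares two groups. That stands, and a reader who infers that the trial plans an analysis without controls goes too far. It does not remove the point, because the text never says which rule for controls was meant, and the obvious one still selects in one arm.

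A second reply is that the sentence on eligible, treated and followed-up participants may only paraphrase the FAS loosely, and that eligibility and follow-up apply to both arms. That is fair. The sentence still conditions on events after randomisation and does not repair 12.2.

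A reader might also infer that the primary analysis requires UC-MSC patients to survive to the third infusion at week 8, which would be immortal time. The text does not support this. The FAS needs one infusion, and 12.3.4 speaks of receiving the assigned treatment, not of completing it. Completion of the regimen is a condition of the PPS only.

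Nor is it established that patients are excluded at the week 0 check with their allocation known. The first visit in 3.3 is undefined: 3.1 places randomisation after enrolment, and Visit 1 in the schedule is week 2. Such exclusion is possible, no more.

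Finally, the bias may be small. If randomisation falls in the 7-day screening window, a constant hazard of −ln(0.60)/60 = 0.0085 per month implies that about 0.2% of an arm, or 0.25 of 125 patients, die before week 0. Larger losses would have to come from refusal, deterioration or failed eligibility, whose prognosis is unknown. If healthier patients refuse (s0 above 0.60), the apparent HR exceeds 1. This stands, and it is why the table is only illustrative.

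**Conclusion.** The definition is wrong as written. Read literally, it leaves no control treated per protocol in the primary analysis set. Read as probably intended, it replaces the randomised comparison with one that drops never-infused patients from the UC-MSC arm only. The second wording in 12.3.4, the two roles given to the PPS, and a time origin at first infusion that controls do not have all leave the primary population and its clock unsettled.

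The size of the bias is unknown. With 5% to 10% never infused, it runs from none (HR 1.00, type I error 5%) if they have the same prognosis as the rest. It passes through HR 0.97 to 0.93 (5.3% to 6.4%) if 40% of them are event-free, and reaches HR 0.90 to 0.79 (8.0% to 18.5%) if none are. This rests on an assumed never-infused rate and prognosis, and on reading 12.1 as 60% event-free at 60 months. A bias in favour of UC-MSC is plausible but not certain. The need to correct the definition does not depend on these figures.

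**What to change.** - In 12.2, define the FAS as all randomised patients, analysed in the arm to which they were assigned, with time zero at randomisation in both arms.
- In 12.3.4, replace the sentence on eligible, treated and followed-up participants with that definition.
- In 7.1 and 9, count survival and HCC-free time from randomisation instead of from the first infusion.
- In 12.2, delete the statement that gives the PPS a role in evaluating primary efficacy, so that it is ancillary throughout, as 12.3.4 already says.
- In 3.3, replace the undefined first visit with a statement that the code is assigned after the final eligibility check.

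The first four are wording changes. The last is operational if codes are now given out earlier. The safety set in 12.2 carries the same infusion condition and needs an entry rule for controls as well.

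The statistical cost is a slight dilution. For example, if 10% of the UC-MSC arm were never infused and fared like controls (assumption), the planned 85% would become 0.90 × 0.85 + 0.10 × 0.60 = 0.825. The HR would move from 0.318 to ln(0.825)/ln(0.60) = 0.377. Power with 100 per group would be Φ((0.225 − 1.96 × 0.0640)/0.0620) = Φ(1.61), about 95%, still above the 80% that 12.1 asks for.

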4.3 Withdrawal criteria

All participants who meet one of the following criteria would withdraw from the trial:

(1) Subject's request to stop test for lack of efficacy, intolerance, adverse reactions, or withdrawal of informed consent by the participants.

(2) Poor compliance (unable to comply with the requirements of the test).

(3) Pregnancy or lactation for women during treatment.

(4) Any complication, adverse event (AE), or laboratory abnormality occurring during the

treatment, which in the opinion of the investigator, indicates that continued participation in the study is not in the best interest of the subject.

(5) Other conditions unsuitable for continuation of the test in the opinion of the investigator.

If participants withdraw from the study because of the occurrence of AEs or laboratory abnormalities, these important event and test results should be recorded in case report form (CRF).

The causes of shedding cases should be recorded in detail. Data involving safety and efficacy should be obtained as much as possible and all end-of-study assessments should be carried out with the subject's consent. All data should be kept intact for reference.

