7.1 Survival analysis

The patients will be followed up for 75 months to record their survival status and survival rate after their first UC-MSC infusion. During the follow-up period, the survival rate of those patients is dependent on the survival status at the last visit point after the first infusion. The time of death of those patients will be recorded and the survival rate will be calculated.

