10.2 Subjects withdraw from the trial

Each participant may, at any time of the study, withdraw from the study for any reason (special or non-special) without being unfairly treated. The subjects who withdraw from the study will not be restricted in their treatment and may continue to receive conventional treatment or other appropriate treatment.

The medical examinations in their screening period should be cancelled for the enrolled patients who fail to be screened into the study, and the reasons for failure should be recorded in the completion/termination page.

If the successfully screened participants withdraw from the clinical trial during the study period, the medical examination for these subjects should be completed at the current visit, and the reasons for quitting the study should be recorded in the completion/termination page.

11 Data Management

This scheme only provides general requirements for data management. Data entry and modification: Data entry and management shall be performed by the data manager of the statistical unit, and will be managed by using an electronic database. To ensure the accuracy of the data, two data administrators are required to input and proofread the data independently.

For questions in the CRF, the data administrator should fill out the question-answer form and ask the researcher. The data administrator will modify, confirm, and enter the data according to the researcher's answers, and can issue the question-answer form again if necessary. The data administrator will import the data into the designated database, hand over the data to the statistician for statistical analysis, and the statistical analysis will write the statistical analysis report.

12 Statistical analysis

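### The missing-outcome rule for the full analysis set (12.2) contradicts itself and, on its natural reading, counts lost patients as events, against the Kaplan–Meier/Cox analysis in 12.3.4

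*Protocol*

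**What the plan says.** The primary endpoints (3.2.1) are survival and HCC-free survival over 75 months. Four places bear on a patient whose outcome is unknown.

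- **12.2**, in the definition of the full analysis set (FAS), which it names as the primary set: where main efficacy indicators are missing, "the missing data is not filled in, and will be assigned to the unresponsive set".
- **12.3.4**: the analysis "will compare the event-free time between the two groups using Kaplan–Meier analysis", with Cox models for the hazard ratio. Follow-up runs "until the date of an endpoint event, death, or the end of the study, whichever occurs first". Censoring is implied by the method but not written out.
- **7.1**: "the survival rate of those patients is dependent on the survival status at the last visit point after the first infusion". The next sentence adds that times of death are recorded and the survival rate is calculated.
- **4.3 and 10.2**, on withdrawal: "All participants who meet one of the following criteria would withdraw from the trial", and for those who leave during the study "the medical examination for these subjects should be completed at the current visit". Section 4.3 also asks sites to gather what safety and efficacy information they can, and to do the final assessments where the patient agrees.

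After week 48, survival and HCC status come from telephone calls at months 24, 48, 60 and 75 (6.10 to 6.13).

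**The concern.** The 12.2 sentence contradicts itself: placing a missing value in an outcome category is a way of filling it in. It also belongs to a responder endpoint. The protocol defines no response for death or HCC, so the only evident way to apply it is to count the lost patient as having had the event. Kaplan–Meier and Cox do something else: the patient contributes time until last contact and is then censored. Because the rule is attached to the FAS, it reaches the primary analysis, and 12.2 and 12.3.4 cannot both be followed.

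The trial is open label (3.3) and controls receive no infusion (3.1), so loss may differ between arms. If losses count as events, a difference in loss becomes a difference in survival. The 7.1 sentence does not settle the matter, since it can mean either that the last status is carried forward or that the patient is censored at last contact.

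**Working it through.** **What the plan gives.** There is no figure for the missing-data rule and no dropout rate. Section 12.1 goes from 100 to 125 per group for dropout or withdrawal. Since 100/(1 − 0.20) = 125, this implies 20% of those enrolled; 100 × 1.25 gives the same number. The 20% is therefore an inference.

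**Assumptions.**
- 60% event-free at 60 months in the control arm, which is a reading of an unclear sentence in 12.1.
- Exponential event times.
- A fraction p of patients with a loss time spread evenly over 0 to 60 months, unrelated to prognosis.
- 125 per arm, with a two-sided 5% two-proportion test of 60-month status.

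**Failure rule.** A patient with a loss time before month 60 fails either way, by an event before the loss or by the loss itself. So the event-free proportion is (1 − p) × 0.60.

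| p | Failure rule | Kaplan–Meier |
|---|---|---|
| 10% | 0.90 × 0.60 = 54% | 60% |
| 15% | 0.85 × 0.60 = 51% | 60% |
| 20% | 0.80 × 0.60 = 48% | 60% |
| 25% | 0.75 × 0.60 = 45% | 60% |
| 30% | 0.70 × 0.60 = 42% | 60% |

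Kaplan–Meier stays at 60% because the loss is assumed to be non-informative.

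**If 7.1 meant last status carried forward.** The mean event-free probability at the loss time is (1 − 0.60)/(−ln 0.60) = 0.40/0.511 = 0.783. At p = 20% the rate is 0.48 + 0.20 × 0.783 = 64%. If 7.1 means censoring at last contact, the answer is 60%.

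**False significance with no true effect.** P(reject) ≈ Φ[(Δ − 1.96 × SE0)/SE1], where SE0 is the pooled and SE1 the unpooled standard error.

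- Loss 10% UC-MSC, 30% control: failing 46% vs 58%, Δ = 0.12. SE0 = √(2 × 0.52 × 0.48/125) = 0.0632. SE1 = √((0.46 × 0.54 + 0.58 × 0.42)/125) = 0.0627. Φ[(0.12 − 0.1239)/0.0627] = Φ(−0.06) ≈ 0.475.
- Loss 15% UC-MSC, 25% control: failing 49% vs 55%, Δ = 0.06. SE0 = 0.0632, SE1 = 0.0631. Φ[(0.06 − 0.1239)/0.0631] = Φ(−1.01) ≈ 0.156.
- Reverse split (30% UC-MSC, 10% control): 42% vs 54%, a false 12-point harm of the same size.

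**Check at 75 months.** This simulation used exponential dropout, 125 per arm and 3,000 replicates.

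- No effect, loss 10% UC-MSC and 30% control: rejection about 39% with the failure rule by two proportions, 41% by log-rank with losses entered as events, and 5% with ordinary censoring.
- Planned effect (85% vs 60% at 60 months), 20% loss in both arms: difference 23.3 points under the failure rule against 29.0 by Kaplan–Meier; rejection about 97% against more than 99%.
- Planned effect, loss 30% UC-MSC and 10% control: difference 9.5 points under the failure rule; rejection about 33% against more than 99%.

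**The case against.** The best defence is that 12.3.4 already names the primary method, that 12.2 begins by saying nothing is filled in, and that exact censoring dates normally belong in the SAP, which is not at hand. This stands in part. Counting losses as events is an inference from an undefined term, and the absence of a written censoring date is not in itself a fault. But 12.2 does not leave the point open. It states a rule for the primary set, and a SAP could adopt ordinary censoring only by setting that rule aside.

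Three stronger readings are tempting, and the protocol does not support them.

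- *That 7.1 is a firm competing rule under which a patient lost alive counts as a survivor.* Section 7.1 never says so. Status at last contact with a date of death is also what Kaplan–Meier needs, so the sentence is ambiguous rather than opposed.
- *That 4.3 and 10.2 end outcome follow-up at withdrawal.* Section 10.2 speaks of the medical examination and does not bar later calls. Section 4.3 asks for efficacy data to be obtained, and 6.14 provides for visits after early withdrawal. Lack of efficacy leads to withdrawal only at the patient's own request, and an adverse event only at that request or on the investigator's judgement.
- *That the plan budgets for 20% loss, or that the bias must favour UC-MSC.* No rate is stated, and the direction depends on which arm loses more patients.

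It is also fair to object that the 47% and 16% figures use a 60-month two-proportion test, which the protocol does not name for the primary endpoints. The 75-month log-rank figure of about 41% shows that the problem does not depend on that test, though the loss split is still assumed.

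**Conclusion.** The concern holds for 12.2. The sentence contradicts itself, does not fit endpoints of death and HCC, and on its natural reading conflicts with 12.3.4. The 7.1 sentence should be cleared up with it because it is ambiguous.

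Applied literally, the failure rule understates event-free survival (48% instead of 60% at 20% loss). Under unequal loss it creates or hides a treatment difference: a false 12-point gap with a 10%/30% split and a false 6-point gap with 15%/25%, in whichever direction the loss runs. Under equal loss the estimates shift but the planned effect would still be detected in most trials.

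All of these sizes rest on assumed loss rates and splits, exponential event times, non-informative loss and the 60%/85% reading of 12.1. The textual conflict depends on none of them.

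**What to change.** - **12.2:** remove the missing-indicator rule for the two primary endpoints.
- **12.3.4:** add, for example: *Patients without an event are censored at the last date known alive (overall survival) or known alive and free of HCC (HCC-free survival).* Keep missing = failure only as a sensitivity analysis, labelled as such.
- **7.1:** reword the last-visit sentence to agree with that censoring rule.
- **4.3 and 10.2, as a clarification:** build on the existing request in 4.3 for efficacy data, and state that the survival and HCC calls at months 24, 48, 60 and 75 continue after a patient stops infusions unless consent is withdrawn.

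The cost is wording, plus telephone calls that are already in the schedule. Sample size, endpoints and primary method do not change.

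### The per-protocol set's role is stated inconsistently, and its completion rule, read naturally, drops early deaths from the UC-MSC arm only: a small bias in a supportive survival analysis

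*Protocol*

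**What the plan says.** Protocol section 12.2 defines three analysis sets. Members of the PPS must, among other conditions, "do not coincide with the major exclusion criteria, complete the treatment regimen", and the definition ends with "PPS will be used to evaluate primary efficacy". The FAS definition just above it says "FAS is the primary analysis set".

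Section 12.3.4 says "The efficacy analysis will be based on the FAS set" and "PPS analysis will serve as an ancillary analysis for FAS", and asks for an explanation if the two sets disagree. Its first sentence on primary efficacy adds a restriction of its own: "All eligible participants who receive the assigned treatment and are followed up will be included in the analysis".

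The UC-MSC regimen is three infusions, at weeks 0, 4 and 8 (synopsis; section 5.3), and the third has a window of ±7 days (section 6.6). Control treatment is guideline-based conventional care with no stated course length or end (sections 3.1 and 5.5). Section 7.1 plans to "record their survival status and survival rate after their first UC-MSC infusion", so the survival clock starts at week 0.

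**The concern.** Completing the regimen is a condition met after randomization. A UC-MSC patient can meet it only by being alive at the third infusion, about 8 weeks after the clock has started. A UC-MSC patient who dies before then is out of the PPS. Nothing in the text removes a control who dies in the same weeks, because open-ended conventional care has no last dose to miss. The UC-MSC arm of the PPS would then contain about 8 weeks in which death is impossible, and the control arm would not.

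UC-MSC patients withdrawn alive during treatment, for example for a complication under section 4.3, would also leave the set.

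At stake is a per-protocol estimate on the primary survival endpoints that leans towards UC-MSC even when the cells do nothing. The stated roles add to the problem: one sentence assigns the PPS to primary efficacy, while two other places give that job to the FAS.

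**Working it through.** **The plan's own figures.** The protocol gives no figure for the PPS. The only event rates are in section 12.1. Its wording mixes a median with percentages; I read it as 60% (control) and 85% (UC-MSC) free of disease events at 60 months. On that reading, 100 per group gives 98.1% power by a two-proportion test, which agrees with the stated power above 80% as a lower bound. The 125 per group equals 100/(1 − 0.20). Neither figure bears on the PPS rule; the 60% rate and the 125 are inputs below.

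**Risk in the first 8 weeks**

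- Control hazard: −ln(0.60)/60 = 0.00851 per month.
- 8 weeks = 56/30.4375 = 1.84 months.
- Event risk: 1 − exp(−0.00851 × 1.84) = 1.55%, and 125 × 0.0155 = 1.9 patients.
- To the end of the third-infusion window (63 days, 2.07 months): 1.75%, or 125 × 0.0175 = 2.2 patients.

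These are events (death or HCC). At this hazard deaths alone cannot exceed them, so 1.6% is an upper figure for deaths.

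**Hand check of the effect with no true difference**

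- Events per arm over 75 months: 125 × (1 − exp(−0.00851 × 75)) = 59.0.
- Remove the 1.94 early events from the UC-MSC arm only: (59.0 − 1.94)/59.0 = 0.967. The person-time lost is negligible, so this approximates the hazard ratio.

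**Simulation with no true difference.** 125 per arm, 75 months, log-rank test. Patients with an event before week 8 are removed from the UC-MSC arm only. The last column is the share of trials that are significant in favour of UC-MSC (nominal 2.5%).

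| Event risk by week 8 | Source of the risk | Hazard ratio | Favouring UC-MSC |
|---|---|---|---|
| any, nobody removed | reference | 1.00 | 2.5% |
| 1.6% | protocol's constant hazard | 0.97 | 3.2% |
| 3% | assumed | 0.94 | 4.4% |
| 4.6% | assumed, early hazard ×3 | 0.90 | 8.0% |
| 5% | assumed | 0.90 | 8.2% |
| 7.5% | assumed, early hazard ×5 | 0.86 | 13.4% |
| 8% | assumed | 0.84 | 14.2% |

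The reference and ×3/×5 rows used 6000 runs, and the 3%, 5% and 8% rows 2000. The 1.6% row was run both ways, giving hazard ratios of 0.973 and 0.968 and 3.2% each time. The simulation standard error near 2.5% is √(0.025 × 0.975/6000) = 0.2 points with 6000 runs and 0.35 with 2000. The excess at the protocol's rate is therefore real but small.

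**Living non-completers (all shares assumed).** Early events are also removed here, and risk varies between patients.

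| Who fails to finish (UC-MSC only) | Hazard ratio | Favouring UC-MSC |
|---|---|---|
| 5% sicker patients (frailty variance 1) | 0.92 | 7.3% |
| 10% sicker | 0.88 | 9.4% |
| 20% sicker | 0.81 | 18.9% |
| 10% at random | 0.96 | 4.0% |
| 10% healthier (frailty variance 0.5) | 0.99 | 3.2% |
| 20% healthier | 1.02 | 2.0% |

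The size, and at the edge the direction, depend on who fails to finish. The protocol gives no information on that.

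**The case against.** The strongest reply is that the PPS carries no primary conclusion. Sections 12.2 and 12.3.4 give that role to the FAS, and the disputed sentence can be read as scope: the PPS is run on the primary endpoints, as an ancillary analysis. This largely stands. A reader might infer that the headline survival result rests on the biased set; the documents do not support that. What remains is a sentence that can be read two ways and is easily repaired.

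Second, the completion wording does not name an arm, section 3.1 lists a regimen for each group, and the withdrawal criteria cover everyone. This also stands in part. The protocol does not say that controls are exempt; the asymmetry is inferred. It is still the natural reading, because the infusions are the only course with a defined end, and the synopsis withdrawal criteria mention failure to receive the infusions, which only UC-MSC patients can have.

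Third, a statistical analysis plan might define completion more fully. But the protocol itself states the rule and the role, so the point concerns what is written.

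Fourth, on the protocol's own rate the effect is slight. That is correct.

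The FAS has a wording problem of its own: it is also defined by receipt of at least one UC-MSC infusion, which read literally leaves no controls. That is a separate and more serious matter, which the change proposed here does not repair.

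**Conclusion.** The point holds in a limited form. Section 12.2 describes the role of the PPS in a way that sits badly with its own FAS statement and with section 12.3.4. Its completion rule, read naturally, also builds immortal time into the UC-MSC arm of a supportive survival analysis.

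At the protocol's implied constant hazard the bias is small: about 2 of 125 patients, a null hazard ratio near 0.97, and 3.2% against 2.5%. This rests on reading section 12.1 as 60% event-free at 60 months, on a constant hazard, and on controls who die early staying in the set.

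A reader might infer that the PPS favours UC-MSC by construction to a material degree. Only the early-death part has a certain direction. Hazard ratios of 0.90 to 0.84 need an early risk of 5% to 8%, which nothing in the protocol supports. For living non-completers the assumed scenarios run from 0.81 to 1.02. The change is worth making because it is cheap, not because the primary result is threatened.

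**What to change.** In section 12.2, replace the last sentence of the PPS definition with the role given in section 12.3.4: the PPS is supportive to the FAS. Then take one of two routes.

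- **Symmetric completion.** Define completion in both arms as having received all assigned treatment due up to death, HCC or the end of the third-infusion window, whichever comes first. Early events then stay in both arms.
- **Common landmark.** Start the PPS at the end of that window (week 8 + 7 days = week 9) in patients of both arms who are alive and event-free then, with the same attendance condition at weeks 0, 4 and 8 for controls. A landmark at week 8 itself would leave up to a week of immortal time.

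The cost is a few sentences and no new data. The per-protocol estimate for UC-MSC may be slightly less favourable. The landmark route also loses the first 9 weeks of events, about 2.2 per arm at the constant hazard. Neither route brings back living UC-MSC patients who stop early, so their number and reasons should be reported beside the PPS result.
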